**BACKGROUND/PURPOSE:**

EUS is well established as a diagnostic tool in the adult population, introduced clinically in the 1980s,[1] but its uses in pediatrics are still emerging. In children EUS is primarily used as a diagnostic tool for evaluation of pancreaticobiliary disease.[2-6]

Pancreatitis has been increasing in incidence in both adult and pediatric populations, requiring providers to increasingly recognize, accurately diagnose and care for patients with ARP and CP[7, 8]

To maximize the success of interventions aimed at slowing or stopping disease progression and ameliorating the deleterious downstream effects of pancreatic insufficiency, techniques capable of identifying the early stages of chronic pancreatic disease are urgently needed.

The advantage of EUS over other diagnostic techniques is the high detail characterization of parenchymal and duct findings of pancreatitis. While adult Rosemont or conventional criteria are in use for EUS diagnosis of CP in adults, validated pediatric criteria do not exist.[9-12] The Rosemont and conventional criteria are nonetheless used for pediatric patients, as there are no reasonable alternatives. To date, EUS findings of CP in children have not been systematically studied.

In addition to grayscale characterization, ultrasound provides the opportunity to quantify tissue stiffness as a biomarker of fibrosis using elastography. Shear wave elastography (SWE) provides operator independent, true quantitation of tissue stiffness and is available on both EUS and transabdominal ultrasound (TUS) systems. Both TUS and EUS SWE have been studied for diagnosis of CP in adult patients,[13-17] however they have not been studied in pediatric pancreatitis.

The Pancreas Care Center at Cincinnati Children's Hospital Medical Center (CCHMC) and the large population it serves places us in a unique position to study EUS and ultrasound elastography in pediatric patients and address these gaps in the literature.

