**SPECIFIC AIMS**

The aims of the proposed study are as follows:

**Aim 1: Characterize endoscopic ultrasound (EUS) findings of pediatric acute recurrent pancreatitis (ARP) and chronic pancreatitis (CP).**

Adult criteria for EUS diagnosis of CP exist, but no such criteria exist for children. As such, the applicability of current diagnostic criteria to pediatric patients is unknown.

**1.1: Catalogue grayscale EUS findings of ARP and CP in a pediatric cohort and compare to healthy controls. Hypothesis:** EUS findings of ARP and CP in pediatric patients will differ from those of adult ARP and CP and will be characteristically different

from healthy controls. *Exp1:* We will catalogue grayscale EUS findings in 40 pediatric patients with known history of ARP or CP undergoing clinically indicated EUS and will compare those with findings in 20 patients without a history of pancreatitis who are undergoing EUS for other indications.

**1.2: Benchmark grayscale EUS against other imaging modalities for diagnosis of CP, particularly early CP, in children.** *Hypothesis:* Grayscale EUS findings will be more sensitive than other imaging modalities in all stages of CP. *Exp2:* We will test associations, in blinded fashion, of grayscale EUS findings catalogued under S.A1.1 in enrolled children with findings on alternative pancreas imaging modalities performed for clinical indications. Specifically, we will correlate to endoscopic retrograde cholangiopancreatography (ERCP), magnetic resonance cholangiopancreatography (MRCP) and computed tomography (CT) performed for clinical indications within +/- 3 months of the EUS.

**Aim 2: Define the diagnostic performance of ultrasound elastography for CP and pancreatic stiffness as a measure of fibrosis in pediatric patients.**

**2.1: Define the diagnostic performance of EUS and TUS elastography for pediatric CP.** *Hypothesis:* EUS and TUS elastography will have high specificity for CP with increased stiffness in patients compared to controls. *Exp 1:* Patients enrolled under Aim 1 will undergo shear wave elastography (SWE) measurement of the pancreas during EUS. These same patients will undergo research TUS with SWE of the pancreas. SWE results by both EUS and TUS will be evaluated for diagnostic performance for CP.

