#### **STUDY DESIGN:**

This will be a single center prospective study to assess the role of EUS and ultrasound elastography in patients with ARP and CP. This pilot study will catalogue EUS and elastography findings in children with ARP and CP and compare with healthy controls.

Additionally, we plan to evaluate sonographic markers for pancreas fibrosis in children, including EUS elastography which we will compare to transabdominal ultrasound elastography for assessment of pancreatic parenchymal stiffness. Elastography and grayscale EUS findings will be benchmarked against parenchymal histology for patients undergoing pancreatic surgery (e.g. total pancreatectomy with islet Autotransplantation).

Data derived from this study including EUS findings in pediatric patients with ARP and CP, and US markers of pancreatic fibrosis, will serve as the foundation for more extensive studies of pediatric pancreatitis with EUS. Additionally, this may serve as preliminary data for establishment of pediatric EUS criteria for CP and early CP.

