### **STUDY PROCEDURES:**

Approximately 60 participants will be recruited to enroll in the study. Forty participants will have ARP or CP as defined by the International Study Group of Pediatric Pancreatitis: In search for a cure (INSPIRE)[18]. Twenty participants from this cohort will be undergoing TPIAT or other pancreatic resection. Another twenty participants will be controls with no history of pancreatic disease undergoing EUS for other clinical indications.

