#### **Statistical analysis:**

*Power calculation:* Given that this is a pilot and feasibility study, a power calculation was not performed. We plan to approach for enrollment all pediatric patients that meet inclusion criteria during the funding period and anticipate no difficulty achieving our recruitment targets based on the robust referral base for our pediatric Pancreas Care Center.

*Aim1:* Frequencies will be used to describe the presence of EUS findings in patients with ARP, CP and controls. Groups will be compared using Fisher's exact and Chi-square tests as appropriate. These tests will also be used, as appropriate to compare the relationship between EUS and other imaging findings.

*Aim2:* Means, standard deviations, 95% confidence intervals will be used to describe TUS and EUS SWE results for patients with ARP, CP and for controls. Agreement between TUS and EUS SWE will be analyzed using Pearson correlations, intraclass correlation coefficients and Bland-Altman analyses. Sensitivity and specificity and 95% confidence intervals will be calculated for diagnosis of CP by SWE using INSPIRE criteria and for prediction of the presence of fibrosis on histology.

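### Aim 2 reduces elastography to sensitivity and specificity: the promised graded fibrosis comparison has no analysis, and no cut-off-free accuracy measure is planned for CP

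*Combined protocol and SAP*

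**What the plan says.** The accuracy analysis for Aim 2 is one sentence in the Statistical analysis section of the combined protocol and SAP: "Sensitivity and specificity and 95% confidence intervals will be calculated for diagnosis of CP by SWE using INSPIRE criteria". The rest of that sentence extends the same measures to histology: "and for prediction of the presence of fibrosis on histology". The same paragraph uses means, standard deviations and confidence intervals to "describe TUS and EUS SWE results for patients with ARP, CP and for controls", so SWE is handled as continuous and three groups are recognised.

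The Aim 2.1 hypothesis under Specific Aims is that "EUS and TUS elastography will have high specificity for CP with increased stiffness in patients compared to controls". Aim 2.3 says SWE will be compared with both binary and semi-quantitative histological fibrosis. The specimen histology paragraph under Study Procedures names a four-stage score. The Procedures and Imaging text takes SWE at four pancreatic sites by EUS (head, genu, body, tail) and three by TUS (head, body, tail).

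On numbers, Study Procedures says "Forty participants will have ARP or CP", with no split between the two diagnoses, plus 20 controls. It adds: "Twenty participants from this cohort will be undergoing TPIAT or other pancreatic resection".

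**The concern.** There are two gaps between what is collected and what is analysed.

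**Fibrosis (Aim 2.3).** A four-stage score is collected and a graded comparison is promised, but the statistical section has only the present/absent version. Children who come to pancreatic resection may nearly all have some fibrosis. The specificity denominator could then be a handful, and the one planned analysis would say little about whether stiffness tracks fibrosis.

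**CP (Aim 2.1).** Sensitivity and specificity of a continuous marker need a cut-off, and none is named. The Background says of SWE in adults, "however they have not been studied in pediatric pancreatitis", so no pediatric value is at hand and a cut-off chosen on the study's own children is likely. Estimates made at a cut-off tuned to the same data are too favourable on average. The result also depends on whether ARP children are compared with CP children, which the plan leaves to inference. The Study Design section says the data "will serve as the foundation for more extensive studies of pediatric pancreatitis with EUS", so optimistic figures could carry into later designs.

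**Working it through.** The plan gives no accuracy target, SWE distribution or power figure, so there is no figure of its own to reproduce.

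**Inputs from the documents:** 40 children with ARP or CP; 20 controls; 20 resected children; four-stage fibrosis score.

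**Assumptions, not in the documents:** 20 CP and 20 ARP; normal SWE with equal SDs; AUC 0.70 to 0.80; lowest histology stage means no fibrosis; 1, 2 or 4 of the 20 resected children fibrosis-free.

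**1. Specificity for fibrosis.** If all n fibrosis-free children are classified correctly, the exact two-sided 95% lower limit is 0.025^(1/n):
- n = 1: 0.025, or 2.5%
- n = 2: 0.025^(1/2) = 0.158, or 16%
- n = 4: 0.025^(1/4) = 0.398, or 40%

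These are the best attainable results.

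**2. Graded against present/absent analysis of the same 20 children.** With one fibrosis-free child, an exact rank-sum test of 1 v 19 has a smallest two-sided p of 2/20 = 0.10, so its power at the 5% level is 0%. By simulation, with stiffness rising 0.5 SD per stage, 1, 2 or 4 fibrosis-free and the others spread about evenly over the higher stages, the present/absent contrast has 0% to 34% power. A rank correlation of SWE with the stage has 44% to 61%.

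**3. Cut-off chosen on the study data for CP.** The simulation uses 20 CP v 20 controls, or v 40 (controls plus ARP, with ARP distributed as controls), one SWE value per child, and the cut-off that maximises sensitivity + specificity.
- Sensitivity is overstated by about 0.07 to 0.09.
- Specificity is overstated by about 0.04 to 0.08.
- Ordinary exact 95% intervals miss the true value at the chosen cut-off in about 3% to 7% of studies in total. Almost all misses have the lower limit above the truth.

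For scale, sampling error alone is larger: 16/20 gives an exact interval of 56% to 94%.

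**4. What AUC would deliver.** The Hanley-McNeil variance, with m CP and n non-CP, is [A(1−A) + (m−1)(Q1−A²) + (n−1)(Q2−A²)]/(mn), where Q1 = A/(2−A) and Q2 = 2A²/(1+A). For A = 0.70 and m = n = 20: Q1 = 0.538, Q2 = 0.576; variance = (0.21 + 0.92 + 1.64)/400 = 0.0069; SE = 0.083; half-width = 1.96 × 0.083 = 0.16. Over A = 0.70 to 0.80 and n = 20 or 40, the half-width is 0.13 to 0.16. No cut-off has to be chosen.

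**5. Effect of the comparator.** Put controls at mean 0, CP at d and ARP at d/2, all with SD 1. AUC 0.70 and 0.80 give d = √2 × Φ⁻¹(AUC) = 0.742 and 1.190. At a fixed cut-off d/2:
- Controls only: specificity Φ(d/2) = 64% and 72%.
- 20 controls + 20 ARP: [Φ(d/2) + 0.5]/2 = 57% and 61%.
- AUC against the combined group falls from 0.70 to 0.65 and from 0.80 to 0.73.

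If ARP stiffness equals that of controls, nothing changes.

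**The case against.** The best defence is that this is a declared pilot without a power calculation, that no success threshold hangs on these estimates, and that small numbers dominate the error. That stands, and it limits the weight of the point.

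Three stronger readings are tempting, and the documents do not support them.

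- *The investigators will tune the cut-off, and perhaps the best site, to their own data.* Nothing says so. An external adult cut-off is not excluded, and no text suggests picking among sites. If the best of three or four sites were picked as well, the sum of sensitivity and specificity would be overstated by 0.16 to 0.24 with 20 CP, but that describes conduct the plan does not mention.
- *The planned confidence intervals are invalid.* Without site picking, total coverage stays near 95%. The fault is that the misses lean to the optimistic side. Compulsory resampling is not justified: with one value per child, cross-validation lowers the root-mean-square error of the sum only from 0.15–0.19 to 0.14–0.17, and bootstrap intervals are much wider (0.41–0.57 against 0.27–0.39).
- *The plan has no non-CP group.* INSPIRE CP status divides the enrolled children, so a fair reading puts ARP with non-CP. The Aim 2.1 hypothesis contrasts patients with controls, which leaves the other reading open. This is ambiguity, not absence.

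The cited histology score may itself define absence of fibrosis, and that cannot be checked here. The defence does not answer the missing graded analysis or the lack of any cut-off-free measure.

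**Conclusion.** The point holds as a low-cost improvement. The firm part is Aim 2.3: a graded comparison is promised and the score is collected, but no graded analysis is planned. The present/absent analysis could leave specificity almost inestimable (lower limit 2.5% to 40% with one to four fibrosis-free children). How many of the 20 will be fibrosis-free is an assumption, as is the rise in stiffness across stages behind the power comparison.

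The second part is conditional. If the CP cut-off is chosen on the study data, the expected overstatement is under 0.10 for each measure, smaller than the sampling error. It rests on a normal model, 20 CP and AUC 0.70 to 0.80.

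**What to change.** Amend the Aim 2 paragraph of the Statistical analysis section:

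1. **Aim 2.3:** add a rank correlation, or an ordinal regression, relating SWE to the four-stage score. Report specificity for presence of fibrosis with its denominator.
2. **Aim 2.1:** make ROC AUC with 95% CI the main accuracy measure. Use one SWE value per child and modality fixed in advance, for example the mean of the available head, body and tail values, which EUS and TUS share. Report AUC separately for CP v controls and for CP v controls plus ARP.
3. **Cut-offs:** label any sensitivity and specificity at a data-chosen cut-off as exploratory and likely optimistic. Resampling correction is optional.

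No new data or visits are needed. The costs are a little more analysis and less favourable headline figures. The EUS genu value is left out of the summary. The graded analysis gains only if stiffness rises across fibrosis stages.

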#### **POTENTIAL RISKS & BENEFITS:**

##### *Potential Risks:*

The risk category for all subjects who choose to participate in the study will fall into the minimal risk category. Participating in the study will add no additional risks to the clinically indicated EUS procedure. There is no known risk from TUS procedure.

##### *Data Safety Monitoring Plan:*

This study is a non-intervention study. Therefore, no formal data safety monitoring board will be appointed. Adverse events related to the study procedures will be monitored by the study coordinator and reported to the PI. The PI will then report any adverse events in writing to the CCHMC IRB within the time frame specified in the IRB guidelines. These procedures should be highly effective in minimizing risk to study participants.

**Potential Benefits:**

There is no direct benefit to the study subject. However, future patients may benefit due to the knowledge gained from this study that may direct future patient care.

**PRIVACY & CONFIDENTIALITY:**

Each subject will be assigned a study ID number. A password-protected table will be maintained that links the study ID number to the medical record number. This table will be maintained on a secure server and/or in a locked file cabinet, as appropriate. The password-protected database containing the research data will be maintained on a secure server with access limited to study personnel. Identifying data will be saved in a password-protected database. No primary data or patient identifiers will be published.

Once the study is complete, data will be retained in a coded state for potential future currently unspecified research. Future research will require IRB approval prior to utilizing this dataset.

**COST OF PARTICIPATION:**

There is no cost to participate in this study.

**PAYMENT FOR PARTICIPATION:**

We will provide each participant/family with a \$75 gift card (Clincard) for reimbursement of patient time and effort to participate in the study and attain the research measurements.

